10.2 Analyses of Secondary Efficacy Endpoints

10.2.1 Secondary Efficacy Endpoints

The secondary efficacy endpoints are:

- Proportion of subjects with ACC count = 0 (ACC grade = 0) at PODs 4, 8 and 15
- Proportion of subjects with Ocular Pain grade = 0 at PODs 4, 8 and 15
- Proportion of subjects with ACF grade = 0 at POD8 maintained through POD15
- Proportion of subjects with ACF grade = 0 at PODs 4, 8 and 15
- Mean change from baseline in ACC grade at PODs 4, 8, and 15
- Mean change-from baseline in Ocular Pain grade at PODs 4, 8 and 15
- Mean change from baseline in ACF grade on PODs 4, 8 and 15
- Number of subjects rescued on or prior to each visit and overall
- Mean change from baseline in best corrected visual acuity (BCVA) by pinhole method using an ETDRS chart at PODs 4, 8 and 15

The ACC count and Ocular Pain grade will be graded using the same grading scale described for primary efficacy endpoints ([Section 10.1.1](#)).

The ACF will be graded as follow:

Grade	Description
0	None
1	Faint
2	Moderate (iris and lens details clear)
3	Marked (iris and lens details hazy)
4	Intense (fibrin or plastic aqueous)

Subjects who meet the rescue criteria may be rescued and placed on an appropriate alternative therapy as determined by the Investigator. The rescue criteria are provided in the [protocol Section 9.4](#).

The ETDRS visual acuity (logMAR score) will be calculated as follows using Original EDTRS Chart 1 and Chart 2:

1. Determine the last row where the subject can correctly identify at least one (1) letter in that row. This is the base logMAR line.
2. Determine the log score for the base logMAR line.
3. Add 0.02 ($T = 0.02$) log units for every letter that is incorrectly identified up to and including the base logMAR line.

10.2.2 Analysis of Secondary Efficacy Endpoints

10.2.2.1 Analysis of Categorical Endpoints of ACC, Ocular Pain and ACF

The secondary efficacy endpoints (categorical endpoints) of ACC grade, Ocular Pain grade and ACF grade will be analyzed and summarized in the same manner as described for the primary efficacy endpoints ([Section 10.1.2](#)). The imputation for missing values for the categorical endpoints is described in [Section 6.4.3.1](#). The proportion of subjects with ACC grade = 0, Ocular Pain grade = 0, and ACF grade = 0 at PODs 4, 8, and 15 will be plotted separately for each of these endpoints.

In addition, the ACC grade, Ocular Pain grade and ACF grade will be tabulated, including the number and percentage of subjects in each grade category, using the observed data only.

10.2.2.2 Analysis of Continuous Endpoints of ACC, Ocular Pain, ACF and BCVA

Mean change from baseline in ACC grade, Ocular Pain grade, ACF grade and BCVA at PODs 4, 8 and 15 will be analyzed using an analysis of covariance (ANCOVA). The ANCOVA model will include treatment as a fixed effect and baseline as a covariate. The imputation for missing values for the continuous endpoints is described in [Section 6.4.3.1](#).

The values of the endpoints and change from baseline at PODs 4, 8 and 15 will be summarized by treatment group using descriptive statistics, including 95% CI for the mean of the change-from-baseline. The adjusted mean of the change from baseline and the treatment difference of adjusted means with associated 95% CI from ANCOVA will be presented. The mean change from baseline with 95% CI at PODs 4, 8 and 15 will be plotted.

In addition, the ACC grade, Ocular Pain grade, ACF grade and BCVA, and change from baseline will be summarized descriptively using the observed data only.

10.2.2.3 Analysis of Endpoint of Rescue Medication Use

The overall number of subjects rescued during the treatment period will be compared between treatment groups using the Pearson Chi-square test. “Rescued during treatment period” is defined as use of rescue medications during the 14-day study drug treatment period. When the treatment

duration of study drug is < 14 days, use of rescue medications will be excluded from the analysis when rescue medications are started > 2 day after the last dose of study drug.

In addition, the cumulative number of subjects rescued at PODs 4, 8, and 15 will be summarized by treatment group and compared between treatment groups using the Pearson Chi-square test at each Analysis Visit. In addition, the number and percentage of subjects rescued in each category of criteria for rescue will be presented for the overall study and at PODs 4, 8, and 15. If multiple rescue medications are used by a subject, only the first time a rescue medication is used will be included in the analysis and summary.

11. SAFETY ANALYSES

The extent of exposure and all safety endpoints will be summarized using the Safety population. For all safety endpoints, the observed data and scheduled visits will be used for summary statistics. No imputation of missing data will be employed.

11.1 Extent of Exposure

Exposure to study drug will be summarized by duration (days) on study drug (the number of days between the first dose date and last dose date of study drug) and total number of doses that are instilled correctly in the study eye using descriptive statistics. In addition, the duration on study drug will be categorized as 1–4 days, 5–8 days, and 9–13 days, and ≥14 days, and the number and percentage of subjects in each category will be presented. The number of doses received per subject will also be categorized as <8 doses, 8–<16 doses, 16–<28 doses, =28 doses, and >28 doses, and the number and percentage of subjects in each category will be presented by treatment group.

If the date of last dose is missing, the date of the last scheduled or unscheduled visit will be used as the date of last dose to calculate the treatment duration.

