6.2.5 Day of Subject Contact on POD14

POD14 is the last day of dosing. Site personnel will contact the subject on POD14 (no specific window) to remind the subject not to take study drug on POD15 and onward and to bring the bottle of study drug and diary back to the clinical site at Visit 5 (POD15). Site personnel will contact the subject using the subject's preferred reliable method of communication, e.g., telephone call, cell phone text or email. The site staff must make an effort to ensure that the subject receives and acknowledges the receipt of the message. Method of contact and whether or not the subject was reached is to be documented in the source document.

Any AEs reported to the site during the POD14 contact must be recorded in the source documents and eCRF. Further assessment of any reported AEs may require an Unscheduled Visit on POD14 if medically significant or they may be assessed, as appropriate, at Visit 5 (POD15).

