6.2.6 Visit 5 (POD15 + 1)

All assessments will be performed as shown in the Schedule of Events ([Table 1](#)).

Ocular assessments will be performed only on the operated, study eye.

Study drug bottle and final diaries will be collected at this visit.

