6.3.4 Study Day and End of Study (EOS)

Study Day for each subject is calculated relative to the date of the first dose of study drug:

- Study Day = Visit Date/Event Date - Date of First Dose +1
When the Visit Date/Event Date is on or after the Date of First Dose
- Study Day = Visit Date/Event Date - Date of First Dose
When the Visit Date/Event Date is prior to the Date of First Dose

Study Day will be used to define analysis windows for efficacy analyses and to evaluate the timing of events or measurements occurring relative to the first dose of study drug.

Study Day ‘-1’ corresponds to Surgery Day 0 and Study Days ‘-29’ to ‘-2’ correspond to Screening Visit (Days -28 to -1) as shown in the Schedule of Events ([Table 2](#)).

EOS is defined as the last visit in the study. EOS will be either Visit 6/POD22 for subjects who complete the study or the Early Termination/Withdrawal visit for subjects who discontinue the study prior to Visit 6/POD22.

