9. TREATMENT COMPLIANCE

Overall treatment compliance per subject for the study eye is defined as:

Treatment compliance (%) = [Total number of doses instilled correctly / (Actual treatment duration) x 2] x100,

where the actual treatment duration is calculated as the number of days between the first dose date and last dose date of study drug.

The treatment compliance will be summarized using descriptive statistics for the Safety population. In addition, the overall treatment compliance will be further categorized as < 80%, 80% – 100% and > 100%, and the number and percentage of subjects with compliance in each category will be presented.

Subject dosing diary data will be listed.

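### SAP 11.1 sets a missing last-dose date to the last visit with no cap, so a Visit 6 attender is given about 22 days of exposure on a 14-day course

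*SAP*

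**What the plan says.** SAP 11.1 measures duration on study drug as "the number of days between the first dose date and last dose date of study drug", and "the duration on study drug will be categorized as 1–4 days, 5–8 days, and 9–13 days, and ≥14 days". When the last-dose date is missing, "the date of the last scheduled or unscheduled visit will be used as the date of last dose to calculate the treatment duration". The sentence covers a visit of any kind. It sets no limit at the end of dosing and does not refer to the diary, the rescue date or any record that drug was stopped.

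SAP 6.3.4 defines the end of study as the last visit and says which visit that is: "EOS will be either Visit 6/POD22 for subjects who complete the study or the Early Termination/Withdrawal visit". Protocol 6.2.7 puts Visit 6 at POD22, plus or minus two days. By then dosing is long over. Protocol 6.2.5 says "POD14 is the last day of dosing", and Protocol 6.2.6 says of Visit 5 that "Study drug bottle and final diaries will be collected at this visit".

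Two groups stop drug but stay in follow-up to POD22: rescued subjects (Protocol 9.4.2) and subjects whose drug is discontinued for persistent IOP elevation (Protocol 9.5.2). Subjects who themselves ask to stop drug are withdrawn and have an Early Termination visit instead (Protocol 6.3).

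SAP 9 uses the same notion of duration in the compliance denominator, "where the actual treatment duration is calculated as the number of days between the first dose date and last dose date of study drug". It gives no rule for a missing date and no reference to 11.1.

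**The concern.** The rule puts the last dose on a day when, by the plan, dosing has ended and the bottle has been handed back. For a completer that is about eight days after the last planned dose and about a week after Visit 5.

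The error also runs in the unhelpful direction. A table of duration on drug is there to show, among other things, how many subjects had a shortened course. A subject who stopped at the first post-randomization visit because of rescue, and whose last-dose date is missing, would appear in the longest category. Rescue is for lack of efficacy (Protocol 9.4.1), so such cases may be unequal between arms, although the documents give no figure for this.

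SAP 9, 6.3.5, 6.4.3.1 and 10.2.2.3 also depend on the last-dose date or on treatment duration. The SAP does not say whether the imputed date is used in any of them.

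**Working it through.** **Inputs.** First dose on POD1, which is Study Day 1 (Protocol 5.1.2.5, SAP 6.3.4). Twice-daily dosing from POD1 to POD14 (schedule of events in both documents). Visit 6 on POD20 to POD24 (Protocol 6.2.7). Duration categories from SAP 11.1. Compliance threshold of 80% from SAP 5.2.

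**The plan's own figure.** A full course is 14 − 1 + 1 = 14 days counted inclusively, with 14 × 2 = 28 doses. This reproduces the stated 14 days. As a plain date difference it is 14 − 1 = 13 days, which would fall in the 9–13 day category. The SAP does not say which count applies.

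**Duration under the rule, for a Visit 6 attender with a missing date.**

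| Visit 6 on | Inclusive | Plain difference |
|---|---|---|
| POD20 | 20 | 19 |
| POD22 | 22 | 21 |
| POD24 | 24 | 23 |

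At the nominal visit the inclusive excess over the course is 22 − 14 = 8 days (6 to 10 over the window). The imputed date is 22 − 15 = 7 days after the nominal Visit 5.

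**Category shifts for those who stop drug but stay to POD22.**

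| Illustrative case | True duration (inclusive) | True category | Category under the rule |
|---|---|---|---|
| Rescued at POD4, last dose POD3 | 3 | 1–4 | ≥14 |
| Rescued at POD8, last dose POD7 | 7 | 5–8 | ≥14 |
| Stopped for IOP, last dose POD10 | 10 | 9–13 | ≥14 |

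A full-course subject stays in ≥14 days on the inclusive count; only the mean and other continuous summaries move.

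**Size.** The documents give no rate of missing last-dose dates. If 1% to 5% of 370 subjects were affected (an assumption), that is 3.7 to 18.5, or about 4 to 19 subjects. Among full-course subjects the mean duration would rise by 0.01 × 8 = 0.08 days to 0.05 × 8 = 0.4 days.

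**Compliance, only if the imputed date is carried into SAP 9.** Taking the intended denominator as duration × 2, a subject credited with all 28 doses scores 28/(2 × 22) = 63.6%. Over the window the inclusive figures are 28/40 = 70.0% to 28/48 = 58.3%; as a plain difference they are 28/38 = 73.7% to 28/46 = 60.9%. All are below 80%.

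**How likely that subject is.** Dose counts and dose dates come from the same diary (Protocol 5.1.2.2, 5.1.2.3). If the last diary, dispensed at POD8, is lost, about 14 or 15 doses remain on record. Over the true 14 days that is 14/28 = 50.0% or 15/28 = 53.6%, already below 80% whatever date is imputed.

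**The case against.** The strongest reply is that little depends on this rule, and much of that reply stands.

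- Every dose is dated in the diary, diaries are checked at POD4, POD8 and POD15, and the data go into the eCRF. Missing last-dose dates should be uncommon.
- A reader might infer that fully dosed subjects will be dropped from the per-protocol population. The documents do not support this. The imputation sentence appears only under Extent of Exposure, and the subject it needs, with 28 recorded doses but no last date, is unlikely because one diary supplies both.
- A reader might infer that all early stoppers count as fully treated. Subjects who ask to stop drug are withdrawn, and their last visit is the Early Termination visit, which can fall before POD14. The shift to ≥14 days concerns those who stop drug and remain in follow-up.
- A reader might infer that the rescue analysis in SAP 10.2.2.3 changes. Its short-duration clause removes only rescue begun more than two days after the last dose. Rescued subjects stop drug at rescue, so they are normally counted either way.
- SAP 11.1 also tabulates dose counts, which do not use the imputed date, and SAP 7.1 separately tabulates subjects who discontinue drug before 14 days.

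None of this defends the rule itself. It is explicit and uncapped, and for anyone who attends Visit 6 it returns a duration that the dosing schedule rules out.

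**Conclusion.** The point holds for the exposure-duration summary. With a missing last-dose date, a Visit 6 attender is assigned 19 to 24 days, depending on the visit day and counting convention, on a course that ends on POD14. A subject stopped early for rescue or IOP but followed to POD22 is placed in ≥14 days. This is a wrong rule, not a missing detail. Its reach is probably small, because it acts only on missing dates and their number is not known.

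Effects on compliance and per-protocol membership depend on carry-over that the SAP does not state. It is also tempting to infer harm to the primary result, but this is not shown: that analysis is on the ITT population, and subjects rescued before the POD15 assessments are non-responders whatever their last-dose date (SAP 6.4.2). The per-protocol analysis is a sensitivity analysis. The SAP should nevertheless settle whether the imputed date is used in its other sections.

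**What to change.** Replace the sentence in SAP 11.1. If the last-dose date is missing, impute the earliest of the following, as applicable: Study Day 14, the rescue start date, the recorded study-drug discontinuation date, and the Early Termination visit date. The imputed date must never be earlier than the last dose recorded in the diary.

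Do not use the last visit on or before Visit 5 as a cap. In an earliest-of rule it would assign POD8 to a subject who dosed to POD14, missed Visit 5 and attended Visit 6. That would give 8 days instead of 14 and, if carried into SAP 9 with 28 doses, a compliance of 28/16 = 175%.

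Under the proposed rule the same subject gets 14 days, and subjects rescued on POD4 or POD8 get at most 4 or 8 days and stay in the 1–4 or 5–8 day category. A rescue date can still be a day later than the true last dose, so a one-day error at a category edge is possible. A subject lost to follow-up without an Early Termination visit or any of the other dates would default to Study Day 14; the SAP should confirm that this is intended.

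In the same edit, state whether the imputed date is used in SAP 9, 6.3.5 and 10.2.2.3 (and 6.4.3.1, which has the same two-day limit after the last dose). State that duration is last date minus first date plus one, and flag imputed subjects in the listing. The cost is a short SAP edit and minor programming; no new data are needed.

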11.2 Adverse Events

Non-serious AEs occurring from the start of study drug administration until EOS will be reported in the eCRF. Serious AEs (SAEs) occurring after signing the informed consent form until EOS will be reported in the eCRF. All AEs will be coded using MedDRA version 23.1 - September 2020, and classified by SOC and preferred term.

All AEs occurring from the start of study drug administration through the last day of participation in the study (EOS) are considered as TEAEs.

An overall TEAE summary by treatment group will be presented by the number of events and the number and percentage of subjects experiencing one or more events, including all TEAEs, treatment-related TEAEs, treatment-emergent SAEs, severe TEAEs, TEAEs leading to discontinuation, and death.

The number and percent of subjects reporting one or more TEAEs and the number of TEAEs will be tabulated by SOC, preferred term, and treatment group for all TEAEs. Results will be displayed in order of decreasing frequency based on the occurrence rate in the APP13007 group,

both across SOC and within each SOC term. Summaries of all ocular TEAEs, ocular TEAEs in the study eye, ocular TEAEs in the non-study eye, all non-ocular TEAEs, TEAEs related to study drug, ocular TEAEs related to study drug in the study eye, non-ocular TEAEs related to study drug, treatment-emergent SAEs, SAEs related to study drug and TEAEs leading to study discontinuation will also be presented in the same manner. The number and percent of subjects reporting one or more TEAEs will also be summarized by maximum severity for all TEAEs, ocular TEAEs in the study eye and non-ocular TEAEs.

The relationship of TEAEs will be determined by the relationship to study drug and/or to the ocular surgical procedure. Ocular TEAEs related to both study drug and surgery or related to surgery only will be summarized separately.

In addition, the incidence of TEAEs occurring in at least 5% of subjects in any treatment group and incidence of non-serious TEAEs above the threshold of 5% of subjects in any treatment group (for data transparency reporting) will be presented.

For summaries by severity of TEAEs, the most severe occurrence for a particular preferred term will be used for a given subject. AEs with missing severity will be considered as ‘Severe’ events for summary purposes, but will be presented as missing in the AE listings.

A TEAE related to study drug is defined as a TEAE with a “Possible”, “Probable” and “Definite” relationship to study drug as defined in [protocol Section 8.3.2](#). These three relationships will be classified as “Related”. For summaries of TEAEs related to study drug, the most related occurrence for a particular preferred term will be used for a given subject. AEs with missing relationship to study drug or surgery will be considered as “Related” for summary purposes, but will be presented as missing in the AE listings.

All AEs will be listed in a data listing. All SAEs (including SAEs for all subjects who sign the informed consent), AEs leading to study discontinuation, and deaths will be listed separately.

A serious and unexpected suspected adverse reaction (SUSAR) is defined in the [protocol Section 8.2](#). The SUSARs will be summarized and listed.

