8.3.4 Action Taken with Study drug

The action to be taken in response to an AE will be to either discontinue or continue study drug.

Subjects will be permitted to restart study drug if there is a temporary interruption of study drug dosing not more than 1 day due to an AE.

Decrease in the dosing frequency or dosing duration of the study drug is not allowed in this study.

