9.5.2 Management

Investigator will use clinical judgment to determine the appropriate IOP-lowering medication to use and when to withdraw study drug and procedures, in consultation with the Study Medical Monitor.

It is important to note that prostaglandin-based IOP lowering medications are prohibited in this study.

- After randomization and start of study drug, if a subject has an IOP > 30 mmHg the Investigator may commence non-prostaglandin-based IOP-lowering medication while continuing the study drug, with appropriate follow-up at the next planned visit or at an unscheduled visit. The subject may require assessment at an unscheduled visit at the investigator's discretion.
 - If the IOP is < 30 mmHg at the next visit, the subject may continue on study drug.
 - If at the next visit, the IOP remains > 30 mmHg while on IOP-lowering medication, then the study drug may be discontinued and alternative IOP-lowering medication may be started, after consultation with the Study Medical Monitor. The subject should continue in the study and complete the assessments indicated in [Table 1](#) through Visit 6 (POD22). The Study Medical Monitor should discuss the persistent elevation of IOP with the Sponsor Medical Monitor.
- After randomization and start of study drug, an IOP of ≥ 21 mmHg **AND** an increase > 10 mmHg from the Visit 2 (POD1)/pre-dose baseline (both criteria must be met) is considered clinically significant and the Investigator should consider starting non-prostaglandin-based IOP-lowering medication while continuing the study drug, with appropriate follow-up at the next planned visit or at an unscheduled visit.
 - If the IOP reduction is satisfactory at the next visit, the subject may continue on study drug.
 - If the IOP reduction of IOP is not satisfactory at the next visit, then the study drug may be discontinued and alternative IOP-lowering medication may be started, after consultation with the Study Medical Monitor. The subject should continue in the study and complete the assessments indicated in [Table 1](#) through Visit 6 (POD22). The Study Medical Monitor should discuss the persistent elevation of IOP with the Sponsor Medical Monitor.

Medications used for treating increased IOP will be recorded in the Concomitant Medications section of the eCRF, noting that they were used to reduce IOP.

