10.3.3 Analysis of Safety

Analysis of safety data will be performed for all subjects in the Safety Population.

Adverse events will be coded using Medical Dictionary for Regulatory Activities (MedDRA) and classified by system organ class and preferred terms. Adverse events will be summarized by total number of TEAEs, number of subjects reporting TEAEs, ocular TEAEs (affecting the study eye and/or the non-study eye and/or both eyes, when appropriate), non-ocular TEAEs, SAEs, serious and unexpected suspected adverse reaction (SUSARs), discontinuing study drug due to an AE, by relationship to study drug and/or ocular surgical procedure, and by severity.

The IOP data for both eyes will be summarized at screening, Visit 6 (POD22)/Early Termination (Withdrawal) visit and change from screening. The observed IOP data and change-from-baseline (POD1) for the study eye will be summarized at each post-surgery visit.

The data for slit lamp biomicroscopy examination endpoints will be summarized at each visit. The summary of change-from-baseline at each post-surgery visit will be presented for the study eye.

Dilated indirect ophthalmoscopic examination findings for the study and non-study eye will be summarized at screening and Visit 6 (POD22)/Early Termination (Withdrawal).

Visual Acuity data will be summarized at each visit. The summary of change-from-baseline at each post-surgery visit will be presented for the study eye.

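### SAP 11.2 tabulates and lists adverse events that led to leaving the study, whereas protocol 10.3.3 asks for those that led to stopping study drug, and in this trial the two can differ

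*SAP*

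**What the plan says.** Protocol 10.3.3 lists the ways in which adverse events will be summarized. The last items in that list are "discontinuing study drug due to an AE, by relationship to study drug and/or ocular surgical procedure, and by severity".

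SAP 11.2 has three outputs on discontinuation:

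- The overall TEAE summary has a row that does not say what is discontinued: "severe TEAEs, TEAEs leading to discontinuation, and death".
- The table by system organ class, preferred term and arm refers to the study: "SAEs related to study drug and TEAEs leading to study discontinuation will also be presented in the same manner".
- The separate listing also refers to the study: "AEs leading to study discontinuation, and deaths will be listed separately".

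SAP 11.2 specifies no table or separate listing for events that led to stopping study drug, and gives no reason for the change of term.

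The protocol treats drug status and study status as different things. Section 8.3.4 puts the response to an adverse event in terms of drug only: "The action to be taken in response to an AE will be to either discontinue or continue study drug". Section 9.5.2, on raised pressure that persists despite IOP-lowering medication, says "then the study drug may be discontinued and alternative IOP-lowering medication may be started, after consultation with the Study Medical Monitor". It then adds "The subject should continue in the study and complete the assessments indicated in" the schedule of events, through Visit 6 (POD22).

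**The concern.** An adverse event can end treatment without ending participation. A table defined by study exit does not count such an event, although it falls squarely within the summary that the protocol asks for. The clearest route to it is the management of raised intraocular pressure, the first corticosteroid-class ocular risk listed in protocol 1.5.1.4 and Table 2.

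This affects how tolerability is reported. Protocol 9.2 permits no dose modification, so an event either stops the drug or does not, and the events that stop it are a natural tolerability measure. If the only discontinuation table by preferred term is tied to leaving the study, a reader could take a nearly empty table to mean that almost no adverse event stopped treatment. The table would not show that.

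**Working it through.** No sample size, power or event count enters this point, so the check is a comparison of texts followed by a traced case.

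**Step 1. Compare the terms.**

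| Output | Event that defines it |
|---|---|
| Protocol 10.3.3 summary | Stopping study drug because of an adverse event |
| SAP 11.2 overall summary row | Discontinuation, unspecified |
| SAP 11.2 preferred-term table | Leaving the study |
| SAP 11.2 separate listing | Leaving the study |

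**Step 2. Can the two events separate in this trial?** Yes. Protocol 8.1.1 makes a post-randomization IOP above 30 mmHg an adverse event, and likewise an IOP of at least 21 mmHg with a rise of more than 10 mmHg from pre-dose baseline. Protocol 9.5.2 then allows study drug to be stopped if the pressure does not respond at the next visit, and keeps the subject in follow-up. Protocol Table 2 also speaks of deciding whether to stop study drug for ocular infection, suspected adrenal suppression, corticosteroid excess and hypersensitivity, without saying that the subject leaves the study.

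**Step 3. Trace one subject.** IOP is above 30 mmHg at one visit and still above 30 mmHg on treatment at the next. Study drug is stopped for that reason before 14 days of dosing, and the subject completes Visit 6 without rescue.

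| SAP output | Is the subject there? |
|---|---|
| 11.2 preferred-term table, study discontinuation | No |
| 11.2 separate listing, study discontinuation | No |
| 11.2 overall row, discontinuation | Cannot be determined |
| 7.1 drug stopped before 14 days, by reason and arm | Yes, but no preferred term, severity or relationship is specified |
| 11.3.1 IOP threshold summary and listing | Yes, as is every subject who crosses a threshold, whether or not drug was stopped |
| 11.2 general TEAE tables | Yes, but not identified as having stopped drug |
| 11.2 listing of all adverse events ("All AEs will be listed in a data listing") | Yes, but no action-taken content is specified |

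**Step 4. What no output supplies.** SAP 7.1 gives the reason without the event, and the TEAE tables give the event without the action. SAP 11.3.1 covers pressure only and does not depend on whether drug was stopped. None of the specified outputs shows, by arm, which adverse events led to stopping study drug.

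**Step 5. Size.** Each such subject contributes 0 to the table and listing in SAP 11.2. With 185 planned per arm, one subject is 1/185 = 0.5% of an arm. The documents give no rate for such stops, so no expected count can be derived from them.

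**The case against.** The strongest reply is that nobody is lost. The traced subject appears in SAP 7.1, SAP 11.3.1, the general TEAE tables and the full listing. SAP 11.3.1 uses the same two pressure criteria that trigger management in protocol 9.5.2. This stands: a reader might infer that the SAP overlooks these subjects altogether, and it does not. The gap is in linking the event to the drug stop.

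Second, the unqualified overall row can be read as study drug discontinuation, which would satisfy the protocol for the headline count. That also stands. The row is ambiguous, not wrong.

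Third, protocol 10.3.3 can be over-read. Relationship and severity are separate items in its list and apply to adverse events generally. The protocol does not promise a preferred-term table or a listing of drug-stopping events broken down in those ways. This is correct, so showing severity and relationship in the new listing is good practice and not a protocol obligation. The drug-discontinuation summary itself is in the protocol's list.

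Fourth, the affected group is narrow. Under protocol 6.3 a subject who asks to stop drug is withdrawn from the study, and 9.1.1.3 allows the investigator to stop drug and withdraw the subject together for deleterious effects. Rescue is not an adverse event. Under 9.5.2 the problem must persist to a second visit, and stopping drug is then optional. Dosing ends on POD14, so the scheduled visits after baseline but within dosing are POD4 and POD8, with unscheduled visits in addition. This limits the likely count but does not remove the mismatch.

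A reader might also infer that the undercount falls mainly on the active arm. The documents do not support that inference. It rests on class risk alone, and protocol Table 2 reports no clinically meaningful drug-related IOP elevation in CPN-201.

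**Conclusion.** The mismatch is real and worth correcting. Followed as written, the SAP's preferred-term table and separate listing omit subjects whose study drug was stopped for an adverse event but who stayed in the study, and the overall row leaves the definition open. These subjects remain visible elsewhere in the planned outputs, but nothing specified identifies the events that stopped study drug, by arm.

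The number affected is unknown and may be small, and the direction of any imbalance between arms cannot be stated. The conclusion assumes only that stops under protocol 9.5.2 are followed to POD22, as that section says. The primary endpoints, sample size, power and alpha are unaffected.

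**What to change.** In SAP 11.2:

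1. Define the discontinuation row of the overall TEAE summary as TEAEs leading to discontinuation of study drug.
2. Add a table by system organ class, preferred term and arm of TEAEs leading to discontinuation of study drug.
3. Add a listing of those events that shows severity and relationship to study drug and to surgery.
4. Keep the existing study-discontinuation table and listing as separate, clearly labelled outputs.

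The cost is one definition, one table and one listing. One check is needed first. Protocol 8.3.4 sets out the permitted actions on study drug but does not say that the action is recorded for each adverse event, so the sponsor should confirm that the eCRF captures it. No clinical rule changes.
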